4.2 Handling of Dropouts

A subject who has been randomized and discontinues study participation prematurely for any reason is defined to be a *dropout* even if no study drug has been taken. Dropouts will not be replaced.

The number of subjects, who prematurely discontinue the study, as well as the reasons for premature discontinuations, will be reported.

The handling of missing data is described in Section 4.3.

4.3 Handling of Missing Data

Missing data introduce ambiguity into the analysis, beyond the familiar sampling imprecision. Even with the best planning and despite best efforts, data may be missing at the end of the clinical trial. All missing or partial data will be presented in the subject data listing as they are recorded in the eCRF, electronic diary (eDiary) or tablet computer.

When appropriate and for a limited number of variables, specific rules will be implemented so as not to exclude subjects or observations from statistical analyses due to missing or incomplete data. The rules are outlined in the following subsections.

4.3.1 Bleeding data

The following rules for the handling of missing vaginal bleeding data pertains to bleeding data assessed by the AH method, the menstrual pictogram (MP, see Appendix 1) or the item "Rate the severity of **any vaginal bleeding** in the past 24 hours" (on a 6-point Likert scale) in the Uterine Fibroid Daily Bleeding Diary (UF-DBD, see Appendix 2). The resulting data forms the basis for the primary, the secondary and bleeding-related other efficacy variables (see Section 6.2).

On days without bleeding, no collection of sanitary products for the AH value determination was asked for. The UF-DBD is used for the identification of these non-bleeding days. Thus, missing AH/MP values on days where the UF-DBD recorded the bleeding intensity as "No vaginal bleeding" or "Spotting" will be set to 0 mL.

Missing bleeding data in the subjects' diaries will be imputed. First, missing bleeding intensities in the UF-DBD will be imputed. Missing bleeding intensities will only be imputed if values are missing for a single or for two consecutive days. For the UF-DBD, a type of 'worst case approach' will be used for imputing missing bleeding intensities. The approach consists in replacing the missing value(s) by the maximum of the bleeding intensities of the day before and the day after the day(s) with missing value(s).

After having imputed missing values in the UF-DBD, missing AH/MP values are imputed in the next step.

For days with bleeding intensity of 'mild' or higher in the UF-DBD, missing AH/MP values will be replaced by the mean value of AH/MP values of the days with the same bleeding intensity. In case there are no AH/MP values with the same bleeding intensity, the mean of the AH/MP values of next higher intensity will be used. In case there is no intensity higher than the bleeding intensity of the missing AH/MP values available, no replacement for the missing AH/MP values will be done for such days, but if at least one such day occurs within the respective 28 days of treatment for a subject, the subject will be considered as not having amenorrhea.

In case blood loss could not be measured by the vendor for a sanitary product, the missing value will be replaced by the mean blood loss measured for the same type of sanitary product for this specific subject.

4.3.2 Dates for MBL assessed by AH method

If there is no information on the dates of reported AH values, the AH values will not be discarded from the analysis. Those AH values will be attributed to the subject's last bleeding episode prior to the date of receipt of the sample at vendor "Laboratorium für Klinische Forschung" (LKF). For this purpose, the total MBL for each date of receipt will be derived using the AH values with missing date. The total MBL will then be added to equal amounts to the AH values of the subject's last bleeding episode prior to receipt of the sample at LKF.

The concrete steps are outlined below:

- (1) The number of days of the bleeding episode with at least 'mild' bleeding will be derived.
- (2) The total MBL will be divided by the number derived in (1).
- (3) The 'mean' MBL derived in (2) will be added to the AH values of all days of the bleeding episode with at least 'mild' bleeding. This step will be performed after having imputed missing bleeding intensities but before having imputed missing AH values (cf. Section 4.3.1). The resulting AH values will not be used for the imputation strategy of missing AH values described in Section 4.3.1.

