### **Start of treatment**

Treatment Period 1 for all subjects will start within Days 3 to 7 of the first bleeding episode following randomization visit. In case a bleeding episode is ongoing at randomization visit, the subject can already start with the intake of study medication during Days 3 to 7 of this bleeding episode. A negative pregnancy test is a prerequisite for starting the study drug (applies to both treatment periods).

Treatment Period 2 will start within Days 3 to 7 of the first bleeding episode following the end of the Treatment Period 1. If no bleeding episode occurs within 7 weeks after end of the previous treatment period, proceed with the induction of bleeding according to Section 9.7.5.

For the start of treatment, subjects will judge based on their experience whether their bleeding episode has started. In case of unusual patterns (eg, start with some days of spotting) subjects should consult with the investigator.

For the statistical analysis, a bleeding episode is characterized by the following entries in the Uterine Fibroid Daily Bleeding Diary (UF-DBD):

- day(s) with bleeding / spotting of which at least one day is of intensity “mild” or higher
- preceded and followed by at least 2 bleed-free days  
(in case the first bleeding episode starts directly after Visit 1, the preceding 2 bleed-free days may not be recorded for this first bleeding episode).

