Furthermore, the last days under treatment with at least 28 days with non-missing bleeding intensity/AH values under treatment until the initial bleeding episode when the treatment started (after the imputations above) (without missing information: Days 57 to 84 under treatment) will be used to calculate the primary efficacy variable and the secondary efficacy variable HMB response. After these imputations a subject will be considered as not having amenorrhea in the presence of missing AH values if the sum of all non-missing AH values is not lower than 2 mL or if for missing AH values the bleeding intensity in the UF-DBD is “mild” or higher, otherwise the subject will be considered as having amenorrhea. An equivalent approach as described for the amenorrhea rate will be applied for the secondary variable HMB response, ie, after the imputations as described above a subject will be considered as not being a HMB responder in the presence of missing AH values if the sum of all non-missing AH values is  $\geq 80$  ml or the reduction of blood loss is  $\leq 50\%$  as compared to baseline or if for missing AH values the bleeding intensity in the UF-DBD is “mild” or higher, otherwise the subject will be considered as a HMB responder.

For the secondary variables onset of amenorrhea and onset of controlled bleeding the first 28 days with non-missing bleeding/AH values until the last 28 days with non-missing bleeding/AH values under treatment will be considered. An analogous approach as described above for the primary efficacy variable and the secondary efficacy variable HMB response will be applied to assess the bleeding status for each of these 28-day windows in terms of amenorrhea and controlled bleeding. If a subject does not achieve amenorrhea or controlled bleeding until end of treatment the subject will be considered as censored for the respective endpoint.

Sensitivity analyses will be conducted to evaluate the impact of missing data. These will be described in the SAP.

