Abbreviations: HMB: Heavy menstrual bleeding, CMH: Cochran-Mantel-Haenszel, H: Hypothesis to be tested related to the amenorrhea (H₁), HMB response (H₂), time to onset of amenorrhea (H₃) or time to onset of controlled bleeding (H₄), TP: Treatment period, A1: Vilaprisan 2mg; 2 treatment periods of 12 weeks, B1: Placebo; 1 treatment period of 12 weeks and Vilaprisan 2mg; 1 treatment period, B2: Vilaprisan 2mg; 1 treatment period of 12 weeks and placebo; 1 treatment period.

The study will be considered successful if at least superiority of vilaprisan 2 mg vs. placebo in Treatment Period 1 (TP1) based on the primary efficacy variable can be demonstrated. In general, superiority of vilaprisan treatment is shown if the respective null hypothesis is rejected to a local alpha level of 0.05 and point estimates of treatment effect favor vilaprisan.

The primary analysis will be conducted based on the FAS (see Section 5.1).

6.2.1 **Primary efficacy variable**

The primary efficacy variable is amenorrhea (yes/no), defined as MBL <2 mL during the last 28 days of treatment. Evaluation of MBL will be based on AH method for a treatment period of interest.

The primary efficacy variable will be derived after the imputation of missing values described in Section 4.3.

If after the imputations described in Section 4.3 and considering potential biopsies, neither of the AH values for the last 28 days are missing, AH values and bleeding intensities of the last 28 days of a treatment period are used to derive the primary efficacy variable.

If, in contrast, there are AH values in the last 28 days of treatment which are still missing (i.e., where an imputation was not possible), it is further studied whether the corresponding bleeding intensities of the UF-DBD are missing on the same day(s) as well.

- (a) If the bleeding intensity is not missing and only the AH value is missing, the bleeding intensity must be at least 'mild', because for 'no vaginal bleeding' and 'spotting' the AH value would have been imputed with 0 mL. Accordingly, it must be assumed that bleeding has occurred on these day(s). Therefore, the subject is considered as not having amenorrhea. Step b) will then not be applied irrespective of whether there are also days for which both, the bleeding intensity and the AH value, are missing.

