- (b) If both, the bleeding intensity and the AH value, are missing for any of the last 28 days, the 28-day period will be extended: The left margin of the 28-day period will be displaced backwards in time and step-wise until the required number of 28 non-missing AH values are included. The left margin may be displaced backwards at maximum up to the end of the first bleeding episode when treatment was started in respective treatment period.

Considering this time window, a subject will be considered as not having amenorrhea if

- i) the sum of the non-missing (i.e. original or imputed) AH values is ≥ 2 mL, or
- ii) there is at least one day with missing AH value and bleeding intensity of 'mild' up to 'very severe' after having applied the imputation rules, or
- iii) the subject did not complete at least 8 weeks of treatment.

If neither of i), ii) or iii) applies, the subject will be considered as having amenorrhea.

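### Undated alkaline hematin volume is assigned to the last diary bleeding episode with no age limit, so spotting loss in the last 28 days can be moved to the bleed at treatment start and the woman counted as amenorrheic

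*SAP*

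**What the plan says.** The primary variable is "amenorrhea (yes/no), defined as MBL <2 mL during the last 28 days of treatment", measured by AH (SAP 6.2.1). Protocol 10.3.3 gives the window as "without missing information: Days 57 to 84 under treatment".

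Four rules decide what happens to a product that reaches the laboratory without a date:

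- **Where the volume goes (SAP 4.3.2).** Undated AH values go to the subject's "last bleeding episode prior to the date of receipt of the sample at vendor". The share per day "will be added to the AH values of all days of the bleeding episode with at least 'mild' bleeding". Nothing limits the gap between receipt and that episode, and nothing requires the episode to lie in the same 28-day window.
- **What counts as an episode.** Protocol 7.1 (Start of treatment) requires "day(s) with bleeding / spotting of which at least one day is of intensity" 'mild' or higher. SAP 4.5 repeats this and makes the diary (UF-DBD) definition the only one used in the analysis.
- **What happens to the spotting days (SAP 4.3.1).** "missing AH/MP values on days where the UF-DBD recorded the bleeding intensity as" no bleeding or spotting become 0 mL.
- **How she is classed (SAP 6.2.1).** She is not amenorrheic if "the sum of the non-missing (i.e. original or imputed) AH values is ≥ 2 mL", if a day rated 'mild' or heavier still lacks an AH value, or if she completed less than 8 weeks. Otherwise she is amenorrheic.

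Protocol 10.3.3 has no rule for undated AH values, and SAP Section 7 does not list this one as a change.

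**The concern.** A spotting-only spell is never an episode, so it can never receive undated volume. If a woman's only loss in the window is spotting and her products are undated, 4.3.2 sends the measured blood to an older episode and 4.3.1 sets the spotting days to zero. The same products with dates would count toward the 2 mL limit, because only missing values are set to 0 mL. The missing date alone then decides the primary outcome.

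The pattern is plausible on vilaprisan. Every subject starts Treatment Period 1 during a bleed (Protocol 7.1). Median onset of amenorrhea on vilaprisan in the earlier data was Day 6 (Protocol 10.4). Protocol 9.6.3.2.7 expects intermittent spotting on treatment. For such a woman the last qualifying episode is often the one at treatment start. At stake are the amenorrhea rate, the treatment difference and, through the same 28-day assessment, time to onset of amenorrhea, which is the third test in the hierarchy.

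**Working it through.** The plan gives no figure to reproduce, because this is a derivation rule. The check applies the rules to example subjects and then sizes the effect.

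**1. How far the volume moves.** Treatment starts on Day 3 to 7 of a bleed (Protocol 7.1). Inclusion criterion 5 offers 12 days as guidance for the longest episode. If treatment starts on bleed day 3, bleed day 12 is treatment Day 10. The shortest move out of the window is then 57 − 10 = 47 days, or 47/7 = 6.7 weeks. The 12 days is screening guidance, so this distance is approximate.

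**2. Example subjects.** The volumes are illustrative: 0.79 mL is the lightest pictogram grade for the normal pad in SAP Appendix 1, not an AH measurement. Three such products give 3 × 0.79 = 2.37 mL and four give 3.16 mL. In cases A to C the starting bleed has its last day above spotting on Day 3, spotting occurs on Days 66 to 69 with four products, and the parcel is received on Day 76.

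| Case | Volume counted in Days 57–84 | Class under the SAP |
|---|---|---|
| A. Products dated | 3.16 mL | Not amenorrheic |
| B. Same products undated | 0 mL (all 3.16 mL goes to the starting bleed) | Amenorrheic |
| C. As B, plus one 'mild' day on Day 60 with 1.0 mL dated | 3.16 + 1.0 = 4.16 mL | Not amenorrheic, correctly |
| D. 1.5 mL undated, truly from spotting on Day 40; 'mild' Day 60 with 1.0 mL dated; received Day 65 | 1.5 + 1.0 = 2.5 mL (true window loss 1.0 mL) | Not amenorrheic, wrongly |

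Cases A and B differ only in the date, yet the outcome reverses. The volume moves at least 66 − 3 = 63 days. Case C shows that one 'mild' day in the window prevents the error. Case D shows the rule acting in the other direction.

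**3. Size.** The documents do not give the number of undated samples, so k, the number of false vilaprisan responders, is an assumption. At the planned 2 × 52 = 104 pooled women, k/104 is 1.0 percentage point for k = 1, 4.8 for k = 5 and 9.6 for k = 10. Protocol 10.4 says the planned size was not reached but does not state the size achieved. If 60 were pooled (an assumption), one woman would be 1/60 = 1.7 points.

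**4. Effect on the test.** This uses the continuity-corrected CMH test on planned strata (52/26/26 vilaprisan, 26/13/13 placebo), with assumed counts and false responders removed from the US stratum.

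| Removed | Start 52/104 vs 5/52: difference, p | Start 82/104 vs 6/52: difference, p |
|---|---|---|
| 0 | 0.404, 2.4 × 10⁻⁶ | 0.673, 7.9 × 10⁻¹⁵ |
| 1 | 0.394, 3.9 × 10⁻⁶ | 0.663, 2.0 × 10⁻¹⁴ |
| 5 | 0.356, 2.4 × 10⁻⁵ | 0.625, 5.6 × 10⁻¹³ |
| 10 | 0.308, 1.7 × 10⁻⁴ | 0.577, 2.0 × 10⁻¹¹ |

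The first scenario is near the planned difference of 0.4. The second is near the regional rates quoted in Protocol 10.4.

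**5. Planned sensitivity analyses.** The per-protocol repeat (SAP 6.2.1.2.1) does not change the derivation. The multiple-imputation analysis (6.2.1.2.2) keeps 0 mL for spotting days. If 4.3.2 applies there too, the woman in case B has a spotting-only diary, a sum below 2 mL and nothing missing. She is then a clear responder and is never imputed or shifted.

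**The case against.** Attribution to an episode is a reasonable default. Protocol 9.4.1 ties the return of products to completion of a bleeding episode, and it has blood loss reported by day and by episode, so dated values should be the norm. A wrong classification needs several things together: undated products, no 'mild' day near receipt, spotting that totals at least 2 mL, and too little dated volume to cross 2 mL anyway. SAP 6.2.3.1 also plans amenorrhea by menstrual pictogram for every 28-day period. The pictogram is entered daily in the eDiary, so it is a dated cross-check. All of this stands and limits the likely frequency. The pictogram analysis is only partial protection: it is descriptive, uses a different measurement and does not correct the primary variable.

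A reader might infer three stronger things that the documents do not support:

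- **That the rule can only create responders.** Case D shows it can also remove one, and Protocol 9.6.3.2.7 expects mild intermittent bleeding as well as spotting on vilaprisan.
- **That the moved loss is known to be recent.** Receipt gives only a latest possible date. Recency is an inference from prompt return.
- **That a single spotting product will usually exceed 2 mL.** The two lightest grades of the normal pad are 0.79 and 1.51 mL. The heavier grades (3.08 mL and above) are less natural for a day rated as spotting.

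**Conclusion.** The point holds as a defect in the stated rule. As written, SAP 4.3.1, 4.3.2, 4.5 and 6.2.1 together can class a woman with at least 2 mL of measured loss in the window as amenorrheic because her products lack a date. The net direction plausibly favours vilaprisan, because placebo women usually have a 'mild' or heavier episode near receipt and spotting-only patterns are expected on vilaprisan. That is a judgement about patterns, not a demonstrated bias.

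The size is about 1 percentage point of the pooled vilaprisan rate per affected woman at 104, and more at the smaller size reached. How many women are affected is unknown. It would be wrong to read this as a threat to the confirmatory conclusion: in the scenarios above p stays at or below 0.0002 even with 10 false responders, though these rest on planned group sizes and assumed counts. What is exposed is the reported rate and difference.

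**What to change.** Amend SAP 4.3.2 before unblinding; SAP 4.6 already provides for amendment after the blind review.

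- Keep the present rule when the last qualifying episode is close enough to receipt to be a plausible source. Fix the look-back limit in advance, for example from the blinded, pooled lag between collection and receipt in dated samples. It must allow for one episode's products arriving in more than one parcel, so the previous receipt date alone is not a suitable cut-off.
- When the episode is older than the limit and the diary shows spotting between it and receipt, add the undated volume to those spotting days before the 0 mL rule is applied. Never add it to days recorded as having no bleeding. The existing 2 mL criterion in 6.2.1 then applies unchanged.
- Report by arm the number of women with undated volume and the number whose class changes.
- Repeat the primary analysis under the 4.3.2 rule as it now stands, as a sensitivity analysis.

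The cost is a small change to wording and derivation and one extra run. The vilaprisan amenorrhea rate may come out slightly lower.

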4.3.3 Ultrasound-related volume measurements

Partially missing data in ultrasound measurements for determining fibroid volume, uterine volume and cyst volume will be handled as described in Section 4.5.

4.3.4 Last study drug intake on eCRF Study Drug Exposure page

Missing dates of last study drug intake on eCRF study drug exposure page used for defining

- the end of a treatment period and the reference end date of treatment phase will be imputed by the date of last study drug intake in the same treatment period reported in the eDiary;
- treatment duration and compliance to study drug will not be imputed (cf. Section 6.1.6).

4.4 Interim Analyses and Data Monitoring

With the implementation of the Integrated Clinical Study Protocol, version 6.0 a safety and efficacy analysis is planned after all subjects have completed their treatment period. All data until 31 DEC 2019 will be cleaned and included in the analysis. The complete efficacy data used for the confirmatory analysis has been collected until this point in time and will be used for the efficacy analysis. Therefore, the confirmatory analysis will be final at this point in time. Additionally, available data up to the time point of analysis will be included in this analysis.

Following this analysis neither the sample size nor the study design will be adjusted. The reason for this is that the confirmatory efficacy analysis will only be performed once and none of the analysis results will trigger decisions on the further conduct of the study, such as an early termination. Therefore, no alpha adjustment or power consideration are required. In addition, no Data Safety Monitoring Board (DSMB) will be required.

The final analysis will follow the end of the study safety closeout visit.

4.5 Data Rules

This section outlines definitions of relevant variables as well as rules for deriving variables. Variables are sorted alphabetically.

Baseline cycle: First day of the baseline cycle is day one of the bleeding episode following Visit 1. The last day of the baseline cycle is the day preceding the next bleeding episode. The baseline cycle length is defined as the number of days from the first day of cycle until the last day of cycle. These definitions will apply if during this cycle the inclusion criterion of HMB diagnosis is fulfilled (MBL >80.00 mL). If HMB is not confirmed in the first bleeding episode following Visit 1 then the second bleeding episode recorded during screening will be considered. Similarly, the first day of the second cycle is the day one of the second bleeding episode following Visit 1 and the day preceding the next bleeding episode will be considered the last day of the cycle. Again, this second bleeding episode will be considered the baseline cycle only if the HMB criterion is fulfilled, otherwise the next bleeding episode, if recorded, will be inspected for the diagnosis of HMB. If none of the bleeding episode spreceding the first drug administration fulfills the HMB inclusion criterion the first bleeding episode following Visit 1 will be considered for the baseline cycle. If no such bleeding episode exists, then the bleeding episode already ongoing at Visit 1, if recorded, will be considered for the baseline cycle, starting with Day 1.

Note that during the screening period the diagnosis of HMB will be inspected using the definition of bleeding episode based on the AH method, as explained in this section and in the protocol. In contrast, during the analysis only the definition of bleeding episode based on the UF-DBD will be used. Therefore, the baseline cycle defined during the analysis here described is independently derived and may differ from the bleeding episode used to assess the HMB diagnosis during the screening period.

Baseline menstrual blood loss (MBL): The baseline MBL is defined as the sum of MBL volume from all days included in the baseline cycle. If baseline cycle length is more than 28

days, only data from the first day of cycle to the 28th day of cycle will be used. If baseline cycle length is less than 28 days or equal to 28 days, data from the first day of cycle to the last day of cycle will be used.

Baseline values and changes from baseline: If an analysis is performed by visits or by Intervals 'Exit Examination' (see *Time Intervals*), the last valid, non-missing value prior to the Reference start date will be considered as baseline value. If the analysis is performed by any time interval different than Intervals 'Exit Examination', the 'worst' measurement will be used, whereby 'worst' is defined for the considered parameter within the specific section.

(*Absolute*) *changes from baseline* will be calculated as the difference between the post-baseline value and the baseline value:

Absolute change = post baseline value - baseline value.

Relative changes from baseline, also referred to as *percent change from baseline*, are derived for some variables. It is defined as

Relative change = $100 \times [\text{post baseline value} - \text{baseline value}] / \text{baseline value}$.

Those baseline definitions apply to the analysis of all TPs. For variables analyzed by 28-day periods, the baseline period corresponds to the last 28 days before Reference start date. This definition does not apply to baseline MBL volume where a specific definition is provided in this section (see *Baseline menstrual blood loss*).

Bleeding episode (assessed by the UF-DBD): A bleeding episode is defined as day(s) with bleeding/'spotting' of which at least one day is of intensity 'mild' or higher, preceded and followed by at least 2 consecutive days with eDiary entry 'no vaginal bleeding'. The preceding 2 bleeding-free days may not be recorded for the first bleeding episode at study entry [1].

This definition of bleeding episode, based on the UF-DBD, will be implemented in the analysis to identify bleeding episodes. The protocol includes a definition of bleeding episode based on the AH method, which will be implemented during the screening period to facilitate the assessment of the HMB inclusion criterion (criterion 5, MBL >80 mL) by clinical sites. This latter definition of bleeding period will not be used in the statistical analysis.

Break period: The break period is defined as the treatment-free period between TP1 and TP2. The break period starts the day following the date of stop date of study drug administration in TP1, and ends the day before the study drug administration starts in TP2. Prior to the Global Protocol Amendment, version 4.0, subjects were instructed to start TP2 within Days 3 to 7 of the first bleeding episode following the end of TP1. If a subject did not start TP2 (due to the temporary pause or for any other reason), the subject does not have any break period but only a follow up period which starts at the first day after the end of TP1. For efficacy variables evaluated within the break period, part of the data from the follow-up period of those patients will be included in the analysis of the break as well. In this case a theoretical end date which reflects the assumed end date of the break period if the subject had started TP2 will be generated. For this purpose information on the start of TP1 will be used: If a subject started TP1 at the i-th Day of her bleeding episode during treatment break. The theoretical end date of the break period will then be assumed as the day before the theoretical start date of TP2.

Endometrial biopsy conducted: A biopsy will be regarded as conducted if the intervention was attempted, either successfully or unsuccessfully. Successful means that the date of biopsy is given and 'Biopsy sample obtained - Not done' is not ticked in the eCRF. Unsuccessful means that the date of biopsy is given, 'Biopsy sample obtained - Not done' is ticked in the eCRF, and the reason 'Unsuccessful attempt' is selected.

Largest fibroid: The largest fibroid is defined as the fibroid with the largest volume at baseline (measured by ultrasound). The fibroid identified at baseline as the largest will be followed up at subsequent visits.

Menstrual blood loss (MBL) for 28-day periods: The MBL for a 28-day period is defined as the sum of MBL (in mL) assessed by AH/MP method in a 28-day period. Non-overlapping, consecutive 28-day periods will be created along the different study periods: screening, treatment periods, break period and FUP. For details about the volume of MBL assigned to MP, see Appendix 1.

Reference start/end dates of treatment phase: The reference start and end dates of treatment phase refer to the first and last study drug intake and will be identified based on the eCRF entry (EXCATN=1). Missing eCRF end dates will be replaced by the date of the last study drug intake according to the eDiary. In case there is no study drug intake recorded in the eDiary, the date of the last available visit will be used, which is the maximum of the last date at which a visit took place (visit end date), and the "last visit" as collected on the eCRF page.

Repeated measurements at the same visit: If more than one post-randomization measurement is available for a given visit, the first observation will be used in the analysis if no special reason for the additional observation was provided in the eCRF.

All observations will be presented in data listings.

Time intervals: Due to the complex visit schedule of the studies, a time-interval based approach is chosen to present data over time. Several time intervals are defined which are used for different analysis topics ('BL/Post baseline', 'Intervals A', 'Intervals B', 'Intervals C', 'Intervals D', 'AE Intervals', 'Exit Examination'). Those are depicted in Figure 4–1. The selection of time intervals used for a certain analysis topic will be described within each section.

BL/Post baseline		BL			Post baseline																
Intervals A		BL			Treatment Phase								FUP Phase								
Intervals B		BL			TP1 + BR					R TP2					FUP1+2						
Intervals C		BL			TP1			BR			TP2			FUP1			FUP2			FUP	
Intervals D	BL	BL	BL	TP1	TP1	TP1	BR	BR	BR	TP2	TP2	TP2	FUP	FUP	FUP	FUP	FUP	FUP	FUP	FUP	
Intervals D	1-28	29-56	57-x	1-28	29-56	57-84	1-28	29-56		1-28	29-56	57-84	1-28	29-56	57-84						
AE Intervals	Pre-	treatr	nent	t "on" (TP1 + 8d) "off" "on": TP2 + 8d "off" Post-treat (Start: day 61									ſ)								
Exit Examination BL, last value E						Exit examination (Start: EoT -7 days);						;									
	with	nin inte	interval									last value within this interval									

Abbreviations: BL: Baseline, TP: Treatment Period, BR: Break, FUP: Follow-up, EoT: End of treatment, d: days.

